8.0 ANCILLARY LABORATORY RESEARCH STUDIES

8.1 Collection of samples

Blood samples: A volume not to exceed 550 ml of peripheral blood will be requested during the initial 8-week period. Subsequent research blood draws will typically consist of < 100 ml of peripheral blood at F/U visits (not to exceed 550 mL in any 8-week period).

Lymphapheresis: A 4-5 liter lymphapheresis procedure for research may be obtained prior to initiating therapy in consenting subjects.

BM biopsies and aspirate: A bone marrow biopsy cylinder and up to 10cc of bone marrow aspirate may be obtained for research at the time of bone marrow biopsy as indicated in sections 6.1 and 6.2.

Lymph node biopsies: An excisional or core lymph node biopsies may be obtained pre-treatment and after treatment. During the course of participating on this study, an additional 10 cc of blood (NIH visits only) and 5 cc of bone marrow aspirate each time a patient has a bone marrow examination may be requested. These samples will be stored with the subject's permission for other exploratory laboratory research studies reviewed and approved by the IRB and listed in Appendix B. Research samples will be coded and stored in the secure laboratory of [name].

8.2 Intended use

These samples will be used for the following intentions.

1. To explore the biologic effects on B- and T-cell subsets and function, we will;
 - Enumerate T (CD4, CD8), B, and NK cells in circulation
 - Characterize T-cell subsets, including T-regulatory cells, Th-1, Th-2, Th-17
 - Characterize T-cell activation state and differentiation
 - Assess expression of checkpoint inhibitory molecules such PD-L1, PD-1, and CTLA-4
 - Genomic profiling of the B- and T-cell repertoire by CDR3 analysis
 - Measure pertinent cytokine and chemokine levels
2. To explore mechanisms of clinical response, we will;
 - Assess shifts in clonal composition on treatment assessed using interphase FISH and gene sequencing for somatic mutations

These specimens will not be used for diagnostic purposes.

Leftover and additional samples will be used for the following descriptive or exploratory ancillary research studies which may be done and if done, may be correlated with the presence or absence of response. Samples may also be sent to Pharmacyclics, an AbbVie Company, once an MTA has been established

8.3 Storage, tracking and disposition of samples and data

Storage: All samples will be stored in the laboratory of [name]. Samples collected will be de-identified prior to storage in the laboratory of the principal investigator following current NHLBI DIR BSI Policy. Efforts to ensure protection of patient information include:

- Each sample is assigned a unique number.
- Vials holding patient samples are labeled with the sequential laboratory accession ID number that does not contain any personal identifier information.
- An electronic database is used to store patient information related to the coded samples
- The laboratory is located in a controlled access building and laboratory doors are kept locked. Visitors to the laboratory are required to be accompanied by laboratory staff at all times.
- Hard copy records or electronic copies of documents containing patient information are kept in the locked laboratory or other controlled access locations.

Tracking: Samples will be ordered and tracked through the CRIS Research Screens. Should a CRIS screen not be available, the NIH form 2803-1 will be completed and will accompany the specimen and be filed in the medical record. Samples will not be sent outside NIH without IRB notification and an executed MTA or CTA.

De-identified human serum and/or plasma and/or tumor samples and clinical data from patients with B-cell malignancies may be sent to [name], Weill Cornell Medical College.

End of study procedures: Samples from consenting subjects will be stored until they are no longer of scientific value or if a subject withdraws consent for their continued use, at which time they will be destroyed.

Loss or destruction of samples: Should we become aware that a major breach in our plan for tracking and storage of samples has occurred, the IRB will be notified.

9.0 BIOSTATISTICAL CONSIDERATIONS

9.1 Primary endpoint:

Primary efficacy endpoint is the rate of complete response at 24 weeks or after 6 cycles. Response to treatment will be determined according to IWCLL 2008 criteria incorporating 2012 and 2013 clarifications pertaining to patients treated with kinase inhibitors.

Primary safety endpoint is the rate of treatment discontinuation within the first 24 weeks or 6 cycles due to intolerable side effects.

9.2 Secondary endpoints:

- Progression-free survival (PFS)
- Overall survival (OS)
- Best response during treatment
- Duration of response
- Minimal residual disease (MRD) state defined by flow cytometry
- Clonal dynamics on treatment assessed using interphase FISH and gene sequencing for somatic mutations
- Shifts in cellular and humoral immunity on treatment (e.g. immunoglobulin levels, myeloid-derived stromal cells, B-cell repertoire, T-cell subsets including regulatory T cells, T helper 1, T helper 2, T helper 17)
- Expression of checkpoint inhibitory molecules such as PD-L1, PD-1, and CTLA-4

9.3 Sample size

The study will enroll 27 evaluable subjects for response assessment for primary efficacy and safety endpoints. Up to 5 additional subjects may be enrolled to account for early discontinuation before completing 6 cycles due to non-treatment related reasons. Those subjects with non-treatment related early discontinuation will not be evaluable for the primary efficacy and safety endpoints.

As for the primary efficacy endpoint, CR with ibrutinib alone has been reported to be 13% in previously untreated CLL population,⁵⁶ and 0-2% in relapsed/refractory CLL.^{54,55} When ibrutinib and rituximab were combined in high-risk CLL patients, CR rate was 8%.⁶¹ Based on the reported data, a CR rate exceeding 20% would generate an interest for further studies. We will use a Simon's minimax two-stage design to test the null hypothesis (H_0) that the CR rate in the study is $\leq 5\%$ against the alternative hypothesis (H_1) that it is $>5\%$ with type I error of 0.05. If the true CR rate is 20%, the study using the following two-stage design has 80% power. In the first stage, we will enroll 13 subjects and assess CR rate after 6 cycles. If there is no CR in these 13 subjects, we will stop the study; if 1 or more CRs are observed, we will enter an additional 14 subjects for a total of 27 evaluable subjects. The null hypothesis will be rejected if 4 or more CRs are observed in 27 subjects. Early discontinuation within the first 24 weeks or 6 cycles due to toxicity related to study drug are counted as non-response towards the primary efficacy endpoint.

As for the primary safety endpoint, treatment discontinuation rate has been reported to be 26% with the treatment with FCR,⁷⁸ in contrast to 4% with the single-agent ibrutinib.⁵⁵ Based on reported data, a treatment discontinuation rate <10% at 24 weeks would favor the improved safety and tolerability of the proposed regimen compared to conventional chemoimmunotherapy. We will use a Simon's minimax two-stage design to test the null hypothesis (H_0) that the treatment discontinuation rate is $\geq 30\%$ against the alternative hypothesis (H_1) that it is <30%. In the first stage, up to 13 subjects will be enrolled: if 3 or more subjects discontinue treatment within 6 cycles due to intolerable side effects, further enrollment will be put on hold and we will request a review by the DSMB. If 2 or fewer subjects discontinue treatment within 6 cycles among the first 13 subjects, an additional 14 subjects will be enrolled for a total of 27 subjects. The null hypothesis will be rejected if 4 or fewer subjects discontinue treatment due to intolerable side effects among 27 subjects. The above design for the primary safety endpoint has a power of 81% and a type I error of 0.05 if the true treatment discontinuation rate is 10%.

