5.5 Holding of Study Drug Administration

5.5.1 Ibrutinib and Surgical Procedures:

Consider the benefit-risk of withholding ibrutinib for at least 3 to 7 days pre and post-surgery depending upon the type of surgery and the risk of bleeding.

5.5.2 Medically Necessary Conditions to Hold Study Drugs:

- If medically necessary reasons to hold ibrutinib occur during treatment (i.e. concurrent infection, impending workups for diagnostic and/or therapeutic purposes), ibrutinib can be held based on the study team's discretion.
- If medically necessary reasons to hold fludarabine occur during treatment (i.e. concurrent infection, emergence of autoimmune cytopenia, impending workups for diagnostic and/or therapeutic purposes), fludarabine can be delayed up to 2 cycles while continuing ibrutinib until the medical reasons to hold fludarabine resolve or return to baseline. If fludarabine is delayed beyond 2 cycles, fludarabine will be omitted and the patient will continue treatment with ibrutinib only.
- Supportive medications including allopurinol, and acyclovir (if indicated) intended to start at cycle 3 will be delayed until fludarabine starts or not given if fludarabine is omitted. Weekly labs intended for cycles 3 and 4 will be delayed until fludarabine starts or not performed if fludarabine is omitted.

5.5.3 Permanent discontinuation of study drug administration in case of treatment related adverse events:

- Serious or life threatening cardiac arrhythmias (grade 3 or 4)
- Severe infection (requiring vasopressor support > 24h, or intubation)
- Any grade 4 toxicity excluding readily reversible metabolic or laboratory abnormalities or hematologic toxicities
- Progressive disease as defined in section 7.3
- Pregnancy or unwillingness to use acceptable method of contraception

Patients who will not be able to receive further study drug administration will be followed for safety and after resolution of the event will continue to be followed at regular intervals and will undergo reassessment of disease as outlined in section 6 and 7.

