6.4 At progression evaluation (see schedule of events Appendix A)

All response assessments as listed in 6.3 may be performed at progression. Additional optional studies may be performed which includes the following:

- Serum protein electrophoresis with immunofixation (SPEP)
- C-reactive protein (CRP)
- PET/CT of the neck, chest, abdomen and pelvis. IV and PO contrast will be used unless the patient has a contrast allergy or impaired renal function
- Peripheral blood interphase FISH with FISH panel containing probes for *ATM* (11q22.3), *D12Z3* (12cen), *D13S319* (13q14.3), *LAMP1* (13q34) and *TP53* (17p13.1)
- IGHV mutational analysis

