9.4 Statistical Methods

The planned analyses will include descriptive statistics on the proportions of overall responses. The response probabilities will be estimated using the sample proportions and their inferences including confidence intervals and hypotheses testing will be evaluated using Binomial distributions, and, if appropriate, normal approximations. The time to responses, overall survival and the PFS time will be analyzed using appropriate nonparametric tools in survival analysis such as Kaplan-Meier estimates taking consideration of random censoring.

In addition, methods based on survival analysis, cumulative incidence rates and other competing risk models will be used to evaluate the treatment effects. Graphical tools will be used to display the appropriate estimates (i.e. estimated proportions and Kaplan-Meier curves) and their corresponding 95% confidence intervals. Methods based on multiple regression, analysis of variance, logistic regression and nonparametric regression will also be employed if deemed appropriate.

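### Section 9.3 drops and replaces early stops for undefined non-treatment-related reasons, so early progression, transformation or unrelated death may leave the CR denominator and bias the CR rate upward

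*Combined protocol and SAP*

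**What the plan says.** Section 9.3 plans 27 evaluable subjects for both primary endpoints: CR after 6 cycles, and discontinuation for intolerable side effects within 6 cycles. It adds: "Up to 5 additional subjects may be enrolled to account for early discontinuation before completing 6 cycles due to non-treatment related reasons". Of that group it says: "Those subjects with non-treatment related early discontinuation will not be evaluable for the primary efficacy and safety endpoints". It fixes an efficacy outcome for one kind of early stop only: those "due to toxicity related to study drug are counted as non-response towards the primary efficacy endpoint".

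The CR test stops at 0 CRs in 13 subjects and rejects a 5% CR rate at 4 or more in 27. The safety rule is: "The null hypothesis will be rejected if 4 or fewer subjects discontinue treatment due to intolerable side effects among 27 subjects".

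Other sections bear on how an early progressor is classed:

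- Section 5.5.3 lists progressive disease under the heading "Permanent discontinuation of study drug administration in case of treatment related adverse events". The same list contains "Pregnancy or unwillingness to use acceptable method of contraception". After the list, it provides for continued follow-up and disease reassessment once drug is stopped.
- Section 6.4: "All response assessments as listed in 6.3 may be performed at progression".
- Section 7, Table 4, has progressive disease as a response category.
- Section 9.7 makes significant progression an off-study criterion, and lets the PI continue ibrutinib for a time in selected cases.
- Section 10.1.3 gives a five-level causality scale. Section 9.5 uses its top two levels, but only for safety stopping.
- Section 9.4: "The planned analyses will include descriptive statistics on the proportions of overall responses". It names no analysis set for the CR rate.

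**The concern.** The rule sorts early stops by whether the drug caused them, not by whether they bear on response. Early progression, transformation or death is a failure of efficacy. If it is classed as not treatment related, the subject leaves the denominator and someone who may still reach CR takes the place. That can only raise the observed CR rate, in a test decided by 4 responses.

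Because the category is undefined and the trial is open-label at a single centre, the classification could be made after the outcome is known. The primary CR estimate, and perhaps its type I error, would then depend on that judgement.

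**Working it through.** **Inputs.** From section 9.3: null 5%, alternative 20%, 0/13 then at least 4/27, and at most 27 + 5 = 32 enrolled. From section 2.6.2: 30-month PFS of 96% on frontline ibrutinib; and, in the series of 40 high-risk patients on ibrutinib plus rituximab (median follow-up 14 months), 4 deaths called unrelated, 1 progression and 1 transplant among those off study. The plan gives no expected rate of outcome-related early stops, so that rate, d, is an assumption throughout.

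**1. The plan's own figures.** P(reject | p) = Σ over x ≥ 1 of P(X1 = x) × P(X2 ≥ 4 − x), with X1 ~ Bin(13, p) and X2 ~ Bin(14, p). At p = 0.05:

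| CRs in stage 1 | Contribution |
|---|---|
| 1 | 0.3512 × 0.0301 = 0.01056 |
| 2 | 0.1109 × 0.1530 = 0.01697 |
| 3 | 0.0214 × 0.5123 = 0.01097 |
| 4 or more | 0.00310 |

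The sum is 0.0416. At p = 0.20 the result is 0.801. The stated type I error limit of 0.05 and power of 80% are reproduced.

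**2. The estimate.** At d = 4%, the expected number of replacements for 27 evaluable subjects is 27 × 0.04/0.96 = 1.1.

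- About one replacement: 4/27 = 14.8% reported, against 4/28 = 14.3% of all treated.
- All five replacements outcome-related: 4/27 = 14.8% (exact 95% CI 4.2 to 33.7), against 4/32 = 12.5% (3.5 to 29.0).

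**3. Type I error.** Set the null at 5% of all treated subjects and let every removed subject be a non-CR. The CR rate among evaluable subjects is then 0.05/(1 − d). The last column allows at most 5 replacements and counts any further such stop as a non-CR.

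| d | 0.05/(1 − d) | No cap | At most 32 enrolled |
|---|---|---|---|
| 0 | 0.0500 | 0.042 | 0.042 |
| 4% | 0.0521 | 0.047 | 0.047 |
| 6% | 0.0532 | 0.050 | 0.050 |
| 6.4% | 0.0534 | 0.051 | 0.051 |
| 10% | 0.0556 | 0.057 | 0.056 |
| 5/32 | 0.0593 | 0.069 | 0.064 |

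The 0.05 level is reached at d of about 5.8%. The source of each assumed rate is as follows.

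- 4% is 100% − 96%, with every event of 30 months placed before cycle 6. This is generous for a frontline population.
- About 6% is 6/40 = 15%, scaled linearly to six months: 15% × 6/14 = 6.4%. Both the scaling and the transfer from a high-risk population are assumptions. Left unscaled, 15% gives 0.063 with the cap.
- 10% and 5/32 are stress values, not estimates.

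**4. The safety rule.** Continue at 2/13 or fewer and reject at 4 or fewer. At a true rate of 30%, type I error is 0.047 with 27 evaluable subjects, 0.057 with 26 and 0.069 with 25. Power at 10% with 27 is 0.809, as planned. Any change for efficacy must therefore not shrink the safety set.

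**The case against.** The strongest reply is that the text does not establish that progressors are excluded. Section 9.3 speaks of being evaluable for response, and progressive disease is a response category in Table 4, so a documented progressor has been assessed and is not in CR. Section 5.5.3 provides for reassessment after drug is stopped. Section 9.7 shows that progression need not end ibrutinib at once. All of this stands, and it is why the point is an ambiguity with a likelier reading. It does not remove the point: none of these sections mentions evaluability, section 6.4 makes assessment at progression permissive, and the 5.5.3 heading cannot classify its entries when pregnancy is among them.

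Secondly, best response is a separate secondary endpoint without the exclusion and would show early progressors as non-CR. That is true, but it is not the CR rate at cycle 6 and does not correct the primary result. Nor do PFS and OS.

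Thirdly, the effect is small at plausible rates. That also stands: about half a percentage point at 4%. Purely administrative withdrawals need not bias the rate at all.

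For safety, removing stops that truly are not toxicity raises the observed discontinuation rate, which is conservative. The safety risk is limited to toxicity stops misclassified as unrelated.

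**Conclusion.** The point holds as an undefined exclusion that can bias the primary CR rate upward. The bias is about 0.5 percentage points with one outcome-related replacement, and at most 2.3 points when 4 CRs are observed and all five replacements are of this kind (14.8% − 12.5%).

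Three stronger readings might be inferred, and the documents support none of them. The first is that the plan definitely excludes progressors; the text leaves this open. The second is that type I error exceeds 0.05. That needs the null to refer to all treated subjects and more than about 5.8% outcome-related stops by cycle 6; if the null refers to evaluable subjects, type I error stays at 0.042. The third is that 14.8% against 12.5% is the expected bias; it is the extreme.

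The opposite inference, that nothing in the documents could take type I error to 0.05, fails as well: the high-risk series, scaled to six months, gives 0.050 to 0.051. Nor is 0.064 a ceiling, since a 20% removal rate gives 0.068 under the same cap. This is a cheap improvement to the plan and does not invalidate the design.

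**What to change.** In section 9.3:

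1. State that any treated subject with progression, transformation or death from any cause before the cycle-6 assessment is efficacy-evaluable, counts as non-CR and is not replaced for efficacy.
2. Limit non-evaluability to a listed set of stops unrelated to outcome and toxicity, such as relocation. Assign second malignancy, withdrawal, noncompliance and transplant in advance. Name the levels of the section 10.1.3 scale that count as treatment related.
3. Keep 27 safety-evaluable subjects for the safety rule, within the existing allowance of 5. The efficacy and safety sets may then differ by a few subjects, so state that the CR test uses the first 13 and then the first 27 efficacy-evaluable subjects in enrolment order.

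In section 9.4:

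4. Report the CR rate among all treated subjects, with an exact 95% confidence interval, beside the primary result.

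**Cost.** This is a rewording plus one added line. The maximum of 32 is unchanged, so the boundaries in sections 9.5 and 9.6 stand. The reported CR rate may be slightly lower. Power stays at 80% if the 20% target applies to all efficacy-evaluable subjects. If it applies only to completers and 4% are early failures, the rate is 0.20 × 0.96 = 0.192 and power is 77%. As under the present text, the allowance runs out if more than 5 of 32 are not safety-evaluable (probability 0.5%, 2.2% or 9.4% at assumed rates of 5%, 7% or 10%). The safety cut-off would then need recomputing.

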9.5 Study Stopping Rules

The study will be monitored to ensure that the occurrence of a specified set of treatment related serious adverse events (TRSAEs) that occur during the treatment period does not substantially exceed an anticipated rate. The following specified TRSAEs determined to be probably or definitely related to therapy will be considered for early stopping of the study

1. Death
2. Severe infection requiring vasopressor >24h or intubation
3. Any grade 4 toxicity **excluding**
 - readily reversible metabolic or laboratory abnormalities
 - hematologic toxicities

We anticipate the rate of these specified TRSAEs within the 6 months period (completion of primary endpoint) to be 15% or less. Following Geller et al. (2003, "Design of Early Trials in Stem Cell Transplantation: A Hybrid Frequentist-Bayesian Approach"),⁷⁹ our stopping rule is determined by a Bayesian approach. The stopping boundary for an experiment is reached if the Bayesian posterior probability that the true probability of developing one or more of the specified TRSAE's exceeds this benchmark rate of 15% is at least 90%. We take our prior distribution to be a beta distribution so that our prior clinical opinion is worth 20% of the weight we will place on the new data. This gives prior parameters $\alpha = 0.9$, $\beta = 5.1$. Hence when we make decisions about stopping the study, the data from the study will dominate over the prior opinion. We begin monitoring the TRSAEs when 3 subjects are evaluable for TRSAEs within the 6 months.

Number of subjects in the experiment	Stop if the number of subjects who have developed any of the specified TRSAE's reaches:
≤ 6	3
≤ 11	4
≤ 16	5
≤ 21	6
≤ 26	7
≤ 32	8

We investigated the performance of the above stopping rule by a simulation study. In each simulation run, we generated a study with 32 independent Bernoulli trials, each had a probability p for having TRSAE and $q=1-p$ for not having TRSAE and compared the TRSAE outcomes with the above stopping boundary to determine whether the study was stopped. We repeated the simulation 100,000 times and computed the proportion of stopped studies (i.e. “number of stopped studies”/100,000) which were stopped using the above stopping rule. The following table summarizes the proportions of stopped studies under a number of scenarios for p :

Probability of TRSAE = p	0.1	0.15	0.20	0.25	0.30
Proportion of Stopped Studies	4.4%	17.9%	41.3%	66.1%	84.2%
Average number of subjects	31.1	28.9	25.1	20.6	16.3

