10.0 DATA AND SAFETY MONITORING

Principal Investigator: Accrual, efficacy and safety data will be monitored by the principal investigator [name]., and by the accountable and medically responsible investigator, [name]., Ph.D.

NHLBI's IRB: Prior to implementation of this study, the protocol and the proposed patient consent and assent forms will be reviewed and approved by the properly constituted Institutional Review Board (IRB) operating according to 45 CFR 46. Quality assurance and control monitoring will be consistent with the NHLBI Division of Intramural Research Clinical Research Quality Assurance and Quality Control Policy.

NHLBI DSMB: The NHLBI Data Safety and Monitoring Board will review the protocol, progress report, accrual, efficacy and safety data at six- or twelve-month intervals as scheduled. All AEs and SAEs observed during the clinical trial and for which there is a relationship with the use of the ibrutinib and fludarabine, or the conduct of the study will be reported to the DSMB at the regularly scheduled DSMB meeting. The DSMB may recommend early termination of the study for considerations of safety and efficacy. We request review by the NHLBI DSMB since this is the first time ibrutinib and fludarabine are being used in combination in a clinical trial.

Pharmacyclics, an AbbVie Company: Pharmacyclics, an AbbVie Company will approve all amendments to the protocol or informed consent prior to submission to the IRB and conduct continuing annual review so long as the protocol is open to accrual or sample and/or data analysis continues. Accrual and safety data will also be monitored and reviewed annually by the IRB. An annual progress report, any amendments to the protocol, and any change in the status of the protocol will be forwarded to [contact].

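### The stated type I error for the safety test (0.05) assumes a binding first stage, but section 9.3 prescribes only a hold and DSMB review at 3 or more of 13 and does not say that this rules out rejection

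*Combined protocol and SAP*

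**What the plan says.** Section 9.3 names a Simon minimax two-stage design for the primary safety endpoint, with a null discontinuation rate of 30% or more and power evaluated at 10%. Its elements are:

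- **Favourable first stage:** "If 2 or fewer subjects discontinue treatment within 6 cycles among the first 13 subjects, an additional 14 subjects will be enrolled", giving 27 in total.
- **Unfavourable first stage (3 or more of 13):** "further enrollment will be put on hold and we will request a review by the DSMB".
- **Final rule:** "The null hypothesis will be rejected if 4 or fewer subjects discontinue treatment due to intolerable side effects among 27 subjects".
- **Claimed properties:** "The above design for the primary safety endpoint has a power of 81% and a type I error of 0.05", the power being at a true rate of 10%.

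The efficacy rule in the same section is worded differently: "If there is no CR in these 13 subjects, we will stop the study". Section 10.0 describes the DSMB's remit in general terms ("The DSMB may recommend early termination of the study for considerations of safety and efficacy") and attaches no consequence to the 3-of-13 boundary. Sections 9.4 to 9.6 do not say what becomes of the safety test if accrual resumes after a hold.

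**The concern.** A Simon design earns its error rates by treating a crossed first-stage boundary as final: the trial ends and the null hypothesis stands. A hold pending review leaves resumption possible. If the trial then runs to 27 subjects, the final rule, read on its own, still permits rejection after 3 of 13 followed by at most 1 of 14, or after 4 of 13 followed by 0 of 14. The stated error rate counts both sequences as failures.

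At stake is an unambiguous conclusion on a primary endpoint. With 3 of 13, a resumption and 4 of 27 at the end, one reading of 9.3 declares the discontinuation rate to be below 30% and the other does not. A hold is not a remote event: the chance of 3 or more of 13 is 13.4% at a true rate of 10% and 79.8% at 30%.

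**Working it through.** **Inputs, all from 9.3.** First stage 13, second stage 14; continue at 2 or fewer; reject at 4 or fewer of 27; null rate 0.30, design rate 0.10. Let X1 ~ Bin(13, p) and X2 ~ Bin(14, p) be the discontinuations in each stage.

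**Step 1: reproduce the plan's figures (binding first stage).** P(reject) = Σ over x = 0, 1, 2 of P(X1 = x) × P(X2 ≤ 4 − x).

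- p = 0.30: 0.00969 × 0.5842 + 0.05398 × 0.3552 + 0.13881 × 0.1608 = 0.0057 + 0.0192 + 0.0223 = **0.0472**.
- p = 0.10: 0.2518 + 0.3510 + 0.2060 = **0.8088**.

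These match the stated 0.05 and 81%.

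**Step 2: let accrual resume after every hold and apply the written final rule.** Two more paths lead to rejection. At p = 0.30:

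- X1 = 3: 0.2181 × P(X2 ≤ 1) = 0.2181 × 0.0475 = 0.0104.
- X1 = 4: 0.2337 × P(X2 = 0) = 0.2337 × 0.0068 = 0.0016.

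Together they add 0.0119. The total equals P(X ≤ 4 of 27) = **0.0591**. If accrual resumes only after exactly 3 of 13, it is 0.0472 + 0.0104 = **0.0575**. At p = 0.10 the probability of rejection becomes 0.8734 (0.8671 with resumption only after exactly 3). The stated 81% therefore fits the binding calculation and not this one.

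**Step 3: vary the chance of resumption.** With the same chance q after every hold, and the efficacy stop ignored, the type I error is 0.0472 + 0.0119q. It reaches 0.05 at q = (0.05 − 0.04716) / 0.01194 = 0.24.

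**Step 4: add the efficacy stop.** No CR in the same 13 subjects ends the study. Assumptions: a subject who discontinues cannot be a CR (9.3 counts toxicity discontinuations as non-response), CR is otherwise independent of discontinuation, and an efficacy stop counts as not rejecting the safety null. For an overall CR rate c, a subject who does not discontinue has CR probability c / 0.7. The path with X1 = x is then multiplied by 1 − (1 − c/0.7)^(13 − x).

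Worked case, c = 0.13: c/0.7 = 0.186, and the multipliers for x = 0 to 4 are 0.931, 0.915, 0.896, 0.872 and 0.843. The sum is 0.0053 + 0.0175 + 0.0200 + 0.0090 + 0.0013 = 0.053 after rounding.

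| CR rate (role in 9.3) | Type I error, binding | Type I error, always resumes | Resumption chance at which it passes 5% |
|---|---|---|---|
| 5% (efficacy null) | 2.7% | 3.3% | never |
| 8% (ibrutinib plus rituximab) | 3.6% | 4.4% | never |
| 13% (ibrutinib alone, untreated) | 4.3% | 5.3% | about 69% |
| 20% (efficacy alternative) | 4.6% | 5.8% | about 33% |
| Efficacy stop ignored | 4.7% | 5.9% | about 24% |

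The always-resume figure passes 5% only above a CR rate of about 10.8%.

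**Step 5: the toxicity stopping rule.** Section 9.5 says: "The following specified TRSAEs determined to be probably or definitely related to therapy will be considered for early stopping of the study". Its events overlap with discontinuations, since 5.5.3 lists among the reasons for permanent discontinuation "Any grade 4 toxicity excluding readily reversible metabolic or laboratory abnormalities or hematologic toxicities". Take the extreme case in which every discontinuation is a 9.5 event and no other 9.5 events occur. The boundaries of 3 within 6 subjects and 4 within 11 then remove 20 of the 286 arrangements of 3 in 13, and 370 of the 715 arrangements of 4 in 13. The added error is 0.01036 × 266/286 + 0.00159 × 345/715 = 0.0096 + 0.0008. The always-resume total is then 5.76% with the efficacy stop ignored, so this rule alone does not bring it below 5%. The 9.6 mortality rule is not modelled; it can only lower the figure.

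**The case against.** The strongest reply is textual. The section names a Simon design, and the only written route to 27 subjects runs through 2 or fewer of 13. The final rule can be read as applying to those 27 alone, and no sentence says that accrual resumes after a hold. This stands as evidence that a binding stage was intended. It does not close the gap, because a hold pending review is not a stop, and the adjacent efficacy rule shows how a stop is written in this protocol.

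The second reply is about size, and much of it stands. The 5.9% needs the DSMB to release every hold, including one after 4 of 13 (31%, above the null rate), and a CR rate at which the efficacy stop seldom acts. A reader might infer that the actual type I error is 5.9%, or that 0.05 can hold only if stage 1 binds or resumption is rare. The documents support neither inference: below a CR rate of about 10.8%, under the assumptions above, the error stays under 5% even if accrual always resumes. The 24% resumption threshold is likewise not a property of the trial as a whole, since it ignores the efficacy stop.

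A reader might also infer a calculation error or a loss of power. There is neither: 0.05 and 81% reproduce for the named design, and resumption raises the probability of rejection at 10%.

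Finally, this is a single-arm phase II study that section 12.3 says is not intended to support a new indication. That limits the consequence. It does not settle what the trial would conclude after 3 of 13 and 4 of 27.

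**Conclusion.** The point holds as a minor one. The stated 0.05 and 81% are those of a binding first stage (4.7% and 80.9%), while 9.3 prescribes a hold and does not say that crossing the boundary precludes rejection. The written rule therefore does not guarantee the stated error rate.

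The worst case exceeds 0.05 by 0.9 percentage points (5.9%), or by 0.75 points if accrual resumes only after exactly 3 of 13. It is reached only with resumption after every hold and a high CR rate. The values by CR rate rest on the independence and non-response assumptions in Step 4. Power at 10% is 80.9% with a binding stage and 87.3% if accrual always resumes, with the other stopping rules ignored. The defect is in the decision rule and not in the calculation.

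**What to change.** Add one sentence to 9.3:

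> If 3 or more of the first 13 subjects discontinue due to intolerable side effects, the safety null hypothesis will not be rejected, whatever the final count; the decision on further accrual remains with the DSMB review.

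This guarantees a type I error of at most 0.05 (4.7%) and matches the stated 81% power. Sample size, cut-offs, stated error rates, enrolment and the DSMB's discretion are unchanged. The price is that power stays at 81% and does not rise to as much as 87%.
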